- The iridocorneal angle must be independently confirmed as being qualified by 2 ophthalmologists using the following criteria:
 - Shaffer Grade ≥ 3 on clinical gonioscopy of the inferior angle
 - Peripheral anterior chamber depth by Van Herick examination $\geq 1/2$ corneal thickness

Note: The independent eligibility assessments must both agree that the Shaffer grade is ≥ 3 and the Van Herick grade is $\geq 1/2$ corneal thickness.

- At the Baseline visit (8:00 AM \pm 1 hour), IOP of ≥ 22 and ≤ 34 mm Hg, with difference between eyes of ≤ 5 mm Hg

Key Exclusion Criteria:

Ocular

- History of previous laser trabeculoplasty
- The following surgical history:
 - a. History or evidence of complicated cataract surgery: eg, surgery resulting in complicated lens placement (such as anterior chamber intraocular lens implant [IOL; sulcus IOL; aphakia etc]) or intraoperative complications (such as a posterior capsular tear [with or without vitreous loss], substantial iris trauma, etc)

Note: history of uncomplicated cataract surgery is not an exclusion.

- b. History of phakic IOL insertion for refractive error correction

Response Measures

Efficacy: IOP measured by Goldmann applanation tonometry

Safety: adverse events, visual fields, visual acuity, macroscopic conjunctival hyperemia, slit-lamp biomicroscopic assessments, dilated ophthalmoscopic assessments (including optic disc assessment), pachymetry, gonioscopy, and specular microscopy

Other: [REDACTED]

General Statistical Methods and Types of Analyses:

Three database locks will be performed: 1) when all patients treated with Bimatoprost SR 10 μ g have completed the Week 24 visit or have prematurely discontinued before the Week 24 visit, 2) when all patients treated with Bimatoprost SR 10 μ g have completed the Month 12 visit or prematurely discontinued before the Month 12 visit, and 3) when all patients treated with Bimatoprost SR 10 μ g have completed the Month 24 visit or prematurely discontinued before Month 24.

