7.3.4 Safety Analyses

Safety analyses will be performed separately for patients in the Bimatoprost SR 15 µg and Bimatoprost SR 10 µg safety populations. The Medical Dictionary for Regulatory Activities (MedDRA) nomenclature will be used to code adverse events and medical history. The number and percent of patients reporting treatment emergent adverse events will be tabulated based on the primary SOC and preferred terms. Summary tables will be generated for all adverse events regardless of causality as well as treatment-related adverse events for the entire study and by treatment cycle. Other safety variables include vital signs (blood pressure, pulse rate, and temperature) and pregnancy test results. Ocular safety will be evaluated through assessment of visual acuity and visual field, evaluation of macroscopic bulbar conjunctival hyperemia and iris color, assessment of endothelial cell density and corneal thickness, IOP measurement, and biomicroscopic and ophthalmoscopic examinations (including gonioscopy with Bimatoprost SR implant assessment, optic disc examination, and dilated fundus examination).

Ocular adverse events and safety variables attributable to each eye will be summarized by Bimatoprost SR or SLT eye, and nonocular safety variables will be summarized by patient.

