9.1 Definitions

9.1.1 Adverse Event

An adverse event is any untoward medical occurrence in a patient or clinical investigation patient administered a pharmaceutical product and that does not necessarily have a causal relationship with the treatment. An adverse event can therefore be any unfavorable and unintended sign (including an abnormal laboratory finding), symptom, or disease temporally associated with the use of a medicinal (investigational) product, whether or not related to the medicinal (investigational) product. This definition includes events related to the medical (investigational) product (Bimatoprost SR implant and applicator combination) or comparator medical device (SLT), and events related to the procedures involved, and also includes any malfunction or deterioration in the characteristics and/or performance of a device. During the screening period, adverse events will be assessed regardless of the administration of a pharmaceutical product.

Note: Adverse events must be collected once informed consent has been obtained, regardless of whether or not the patient has been administered study treatment.

Progression of treatment indication including new or worsening of anticipated clinical signs or symptoms, which are collected as clinical efficacy variables and assessed as unequivocally associated with the disease progression and /or lack of efficacy, should NOT be reported as adverse events unless the disease progression is greater than anticipated in the natural course of the disease.

IOP return to baseline following the cessation of the Bimatoprost SR treatment effect should not be considered an adverse event.

Adverse events will be assessed, documented, and recorded in the eCRF throughout the study (ie, after informed consent has been obtained). At each visit, the investigator will begin by querying for adverse events by asking each patient a general, nondirected question such as “How have you been feeling since the last visit?” Directed questioning and examination will then be done as appropriate. All reported adverse events will be documented on the appropriate case report form.

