10.0 EFFICACY ASSESSMENTS

The primary efficacy measurement is IOP at Hour 0, which will be measured in each eye using the Goldmann applanation tonometer. Two consecutive measurements will be taken for each eye. If the first 2 measurements differ by > 1 mm Hg, a third measurement will be taken. The IOP value for a given eye will be the median of all measurements, and this is consistent with the protocol IOP description in Study Protocol Section 6.1.1 (If the first 2 measurements differ by ≤ 1 mm Hg, the IOP for the given eye will be the average of the 2 readings. If the difference between the first 2 measurements is > 1 mm Hg, the IOP for the given eye will be the median of the 3 readings). For consenting patients at selected sites, additional IOP data will be collected at Hour 2 and 8, and these data will be included in diurnal IOP analyses.

Unless specified otherwise, the IOP measurements obtained after initiating the use of non-study IOP-lowering treatment (medications or procedures or both) in an eye will be excluded from the efficacy analysis.

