11.0 SAFETY ANALYSES

All safety analyses will be performed using the safety population. Unless otherwise stated, the last non-missing safety assessment before the SLT treatment (Day 1) will be used as the baseline for all analyses of that safety parameter. As indicated in Section 6.4, safety data collected at Screening for eligibility assessment will not be analyzed.

All safety analyses described in the section 11.0 will be performed both Bim SR 10 µg and Bim SR 15 µg.

Ocular safety will be evaluated through; ocular AEs, best corrected visual acuity, visual field examination, specular microscopy, macroscopic iris color assessment, macroscopic conjunctival hyperemia assessment, gonioscopy/angle assessment, biomicroscopy (using a slit lamp), lens assessment, optic disc examination, dilated ophthalmoscopy, pachymetry, and anterior segment-optical coherence tomography.

Non-ocular safety analysis includes non-ocular adverse events (AEs), clinical laboratory results, vital signs (blood pressure, pulse rate and temperature), and pregnancy test results.

Safety analyses will be summarized by study periods. Analysis study periods are defined as follows:

- **During the study:** Date of SLT treatment through Month 24/Exit visit/last study visit available.
- **Analysis Cycle 1:** SLT Treatment date (Day 1) through the second Bim SR administration date – 1. If the second Bim SR administration was not given to a patient, all safety assessments through Month 24/Exit visit/last study visit available will be included in analysis cycle1.
- **Analysis Cycle 2:** Second Bim SR administration date through Month 24/Exit visit – 1.
- **Analysis Cycle 3:** Third Bim SR administration date through Month 24/Exit visit – 1, valid for only Bim SR 15 µg.

All summaries will be based on the first treatment received in each eye (Bim SR or SLT). If a patient who received both SLT and Bim SR in the same eye, safety assessments will be summarized in Bim SR. For non-ocular safety measures, overall summaries will be presented regardless of study treatment. For ocular safety assessments, summaries will be presented for the periods of during the study, Analysis Cycle 1 and Analysis Cycle 2 as shown in Figure 11-1 below.

Figure 11-1 Analysis Cycle Illustration

| Treatment Schedule | Cycles for Safety Data Analyses | |
|--|---------------------------------|------------------|
| | SLT eye | BIM SR eye |
| Day 1, SLT administration | Analysis Cycle 1 | Analysis Cycle 1 |

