17.3 ANALYSIS WINDOWS

[Table 17-1](#) provides an overview of efficacy and safety assessments with visit schedule and analysis window table for by-visit and by-cycle analysis.

Table 17-1 Visit Schedule, Visit Windows and By-Cycle Analysis for Efficacy and Safety Assessments

| Efficacy/Safety Assessments | Visit Schedule | Visit Window for by-visit and Analysis Cycle Analysis |
|---|--|--|
| Hour 0 IOP | Baseline, Day 2, W4, W8, W12,W15, W20,W24,W28,W31,W36,W40,W44, W47,W52, M13, M14,M15,M16,M18, M20,M22, M24/EXIT | Table 17-2 |
| Macroscopic conjunctival hyperemia | Baseline, Day2, W4,W8,W12,W15, W20,W24,W28,W31,W36,W40,W44,W47 ,W52,M13,M14,M15,M16,M18,M20,M22 , M24/EXIT | Table 17-2 |
| BCVA | Baseline, Day 2, W4, W8, W12, W15, w20,W24,W28,W31,W36,W40,W44, W47,W52,M13,M14,M15,M16,M18,M20, M22,M24/EXIT | Table 17-2 |
| Visual field | Baseline, W24,W52,M18,M24/exit | Table 17-4 |
| Specular microscopy | Baseline, W4, W12, W24, W40, W52,M16,M20, M24/Exit | Table 17-3 |
| Biomicroscopy | Baseline, Day2, W4, W8,W12,W15, W20,W24,W28,W31,W36,W40,W44, W47,W52, M13,M14,M15,M16,M18, M20,M22, M24/EXIT | Overall by-cycle summary |
| Gonioscopy/ Angle assessment | Baseline,W4(optional),W8,W12(optional), W15,W20,W24(optional),W28,W31,W36, W40,W44,W47,W52,M13,M14,M15,M16, M18,M20,M22,M24/EXIT | Table 17-2 |
| Pachymetry | Baseline, W4, W12, W24, W40, W52, M16, M20, M24/EXIT | Table 17-3 |
| Optic disc/ Ophthalmoscopy/ Lens assessment | Baseline, W12, W24, W40, W52, M16, M20, M24/EXIT | Table 17-3 |

[Table 17-2](#) presents the visits assigned for by- visit and analysis cycle analyses of the efficacy (Hour 0 IOP), and safety assessments that occur every month (or 2 months after 1-year of follow-up after the first Bim SR administration), including of macroscopic conjunctival hyperemia, best-corrected visual acuity, biomicroscopy, and gonioscopy/angle assessment. [Table 17-3](#) presents the visit assigned for by-visit and analysis cycle that occur every 3 or 4 months, including of specular microscopy, pachymetry and optic disc assessments which occur every 3 or 4 months. [Table 17-4](#) presents the visits assigned for by-visit and analysis cycle analyses of visual filed, ophthalmoscopy, optic disc, and lens assessments which occur every 6 months.

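### Protocol 7.3.4 names IOP as an ocular safety measure, but the SAP defines no IOP safety summary and its efficacy tables cover IOP rises only in part

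*Protocol*

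**What the plan says.** Protocol 7.3.4 (Safety Analyses) lists the components of ocular safety, including "assessment of endothelial cell density and corneal thickness, IOP measurement, and biomicroscopic and ophthalmoscopic examinations", and says that safety variables belonging to an eye will be summarised by Bimatoprost SR or SLT eye.

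The SAP's counterpart, Section 11.0, begins "Ocular safety will be evaluated through; ocular AEs, best corrected visual acuity, visual field examination, specular microscopy, macroscopic iris color assessment" and, after conjunctival hyperemia, ends with "gonioscopy/angle assessment, biomicroscopy (using a slit lamp), lens assessment, optic disc examination, dilated ophthalmoscopy, pachymetry, and anterior segment-optical coherence tomography". IOP is not in it. SAP 17.3 classes IOP as an efficacy variable when it introduces the window table: "analyses of the efficacy (Hour 0 IOP), and safety assessments that occur every month".

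The protocol is not consistent with itself. The Response Measures part of its Summary gives IOP as the efficacy measure and starts the safety list "Safety: adverse events, visual fields, visual acuity, macroscopic conjunctival hyperemia, slit-lamp biomicroscopic assessments, dilated ophthalmoscopic assessments", without IOP anywhere in that list. Section 6.2 (Safety Measures) does not list IOP either.

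Two further sets of rules decide where an IOP rise can appear.

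- SAP 10.0: unless otherwise specified, IOP obtained after non-study IOP-lowering treatment has begun "in an eye will be excluded from the efficacy analysis".
- Protocol 9.1.1: "IOP return to baseline following the cessation of the Bimatoprost SR treatment effect should not be considered an adverse event". It also says that signs collected as efficacy variables, if judged unequivocally due to lack of efficacy or to progression, "should NOT be reported as adverse events unless the disease progression is greater than anticipated in the natural course of the disease".

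**The concern.** The protocol treats raised IOP as a hazard of the procedures. Section 5.3 mentions an acute spike after SLT, 5.9.2.3 tells the investigator to treat one if it is seen, and 4.2.1 refers to IOP elevation with microhyphema. A by-eye safety summary of measured IOP is therefore what a reader of 7.3.4 would expect. If the SAP is followed as written, that summary is not produced. The comparison of IOP rises between the two eyes would then rest on efficacy tables built to show lowering, on adverse events reported at the investigator's discretion, and on the start of other treatment.

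Iris colour has a similar gap. SAP 11.0 lists it as an ocular safety measure, but the only summary defined is the baseline one in SAP 8.1.

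**Working it through.** There is no planned figure to reproduce. The check sets the sections side by side and counts visits.

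**1. Safety sections.** SAP 11.3.1 to 11.3.10 cover pregnancy, visual acuity, visual field, hyperemia, specular microscopy, pachymetry, biomicroscopy with ophthalmoscopy, optic disc, lens, and gonioscopy with implant assessment. IOP subsections: 0 of 10.

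**2. Scheduled Hour 0 visits (SAP Table 17-1).** Day 2 (1) + Weeks 4, 8, 12, 15, 20, 24 (6) + Weeks 28, 31, 36, 40, 44, 47, 52 (7) + Months 13, 14, 15, 16, 18, 20, 22, 24 (8) = 22 post-baseline visits.

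**3. Named IOP-change summaries for 10 µg.** SAP 10.1 gives Weeks 4, 12 and 24; SAP 10.2.4 gives Weeks 8, 15 and 20. That is 6 of 22, leaving 22 − 6 = 16: Day 2 and the 15 visits after Week 24.

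**4. What the planned tables can show for 10 µg.**

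| Reading | Planned use | Can it show a rise? |
|---|---|---|
| Day 1 post-SLT | None; Protocol 5.9.2.3 rules it out for efficacy and Table 17-1 has no Day 1 IOP | No |
| Day 2 | Tables of eyes with ≥15%, ≥20% or ≥30% reduction (SAP 10.2.3, 10.3.3) | No |
| Weeks 4, 8, 12, 15, 20, 24 | Descriptive change; reduction tables; MMRM at Weeks 4, 12, 24 | Only as the mean and extreme value at that visit |
| Week 28 to Month 24 | Reduction tables | No |
| After non-study treatment | Sensitivity MMRM (SAP 10.4.3) | Only as a mean difference at Weeks 4, 12, 24 |

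SAP 10.4.3 refers to all available Hour 0 data but applies the Section 10.1 model, whose analysis visits are Weeks 4, 12 and 24. The OAG/OHT subgroup summary (SAP 12.1) names no visits, so it cannot be counted on for the later ones. Protocol 7.3 includes the maximum in descriptive statistics, so the six-visit tables would show the single largest change at each visit. No table counts eyes with a rise or gives each eye's largest rise over follow-up.

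**5. The 15 µg group.** SAP 10.3.5 summarises change from baseline at each visit. It uses the ITT population and is subject to the same default exclusion of IOP after non-study treatment, so it is not a safety summary either.

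**6. Population.** Efficacy follows the randomised eye (SAP 6.1). Safety follows treatment received (SAP 6.3). An efficacy table is therefore not a by-treatment-received table.

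**7. Iris colour.** Collected after baseline at Weeks 4, 12, 24 and 52 and Months 18 and 24 (Protocol Tables 3 to 6), six visits. It has no change analysis and no row in SAP Table 17-1.

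**The case against.** The strongest case against is that rises do have routes into the report, and much of it stands.

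- **Adverse events.** A reader might infer that many IOP rises are kept out of the tables. The documents give no rate of rises, spikes or rescue, so that does not follow. Protocol 9.1.1 excludes return to baseline and unequivocal lack of efficacy; it does not bar a procedural spike or a rise above baseline. Once reported, such an event is tabulated by eye and cycle in SAP 11.1, with tables for events within two days of administration and for the interval between SLT and the first implant. What remains is that reporting depends on judgement without a numeric threshold, by an investigator who is unmasked (Protocol 9.4).
- **Rescue.** A reader might also infer that the comparison of rises cannot be reported at all. That is too strong. The exclusion begins only after non-study treatment starts, so the rule does not itself remove the triggering reading. Time to that treatment is analysed by Kaplan-Meier (SAP 10.2.2), and the medications are summarised by eye (SAP 8.4.2). Rises that do not lead to treatment are not covered this way.
- **Lost readings.** One could count the 17 scheduled visits from Week 20 to Month 24 and say that an eye rescued just before Week 20 loses all but Week 24. This counts readings in one hypothetical eye, not rises. Some patients treated in both eyes may skip Months 13, 15 and 22, and the readings stay in the database. It is not a measure of harm.
- **Intent.** Windows for Hour 0 IOP run to Month 24 and SAP 17.5 promises listings, so later summaries may be intended. The SAP does not define them, and a listing is not a summary.
- **Comparability.** The Day 1 post-SLT value is a single reading that need not be masked, taken around apraclonidine or brimonidine. Pooling it with masked two-person Hour 0 values would be unsound. This stands and shapes the fix.

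**Conclusion.** The mismatch is established: Protocol 7.3.4 commits to IOP as an ocular safety evaluation by eye, and the SAP defines none. The protocol's own Summary and Section 6.2 disagree with 7.3.4, so the passages must be reconciled whichever way the sponsor decides. The efficacy tables do not substitute. For 10 µg, 16 of 22 scheduled post-baseline visits have no named IOP-change summary, and no table counts rises. The 16 of 22 describes table coverage, not the frequency of rises.

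This rests on reading SAP 10.4.3 as confined to the visits of the Section 10.1 model, and on no IOP safety table being specified outside these documents. The matter is descriptive: the primary noninferiority inference, its power and its sample size are unaffected.

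**What to change.** Add an IOP subsection to SAP 11.3, on the safety population, by treated eye and analysis cycle, for both dose groups.

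- Use masked Hour 0 IOP, with the Baseline-visit Hour 0 value named as baseline. The general rule in SAP 11.0 (last value before SLT) could be read to admit the single preoperative Day 1 reading, although the Table 17-2 baseline window points the other way.
- Report the largest increase from baseline per eye and the number of eyes exceeding rise thresholds fixed before the primary lock. Show both with readings after non-study treatment included and, separately, excluded. Include Day 2.
- Put the Day 1 post-SLT readings in a separate table if the eCRF captured them. Protocol Table 2 shows no Day 1 IOP entry, so this needs checking.
- Add an iris-colour change table for the measure SAP 11.0 already lists.
- Align the Protocol Summary and Section 6.2 with 7.3.4. If IOP is not meant to be a safety measure, say so in the SAP with the reason and amend 7.3.4 instead.

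The cost is SAP and protocol wording and a few extra descriptive tables. The Hour 0 and iris-colour assessments are already scheduled.

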7.4 Subgroup Analyses

A subgroup analysis will be conducted for patients who received Bimatoprost SR 10 µg administration under the flexible dosing regimen as specified in the protocol. This will include patients enrolled under Amendment 6 and patients who were reconsented to Amendment 6 before receiving the second Bimatoprost SR administration.

The details of this subgroup analysis will be provided in the Statistical Analysis Plan.

7.5 Sample Size Calculation

The sample size calculation is based on paired-eye differences using a normal approximation with a 2-sided significance level of 0.05, assuming that there is no difference in mean IOP change from baseline between Bimatoprost SR 10 µg eyes and SLT eyes and that change from baseline in IOP has a standard deviation of 4 mm Hg. A sample size of 144 patients treated with Bimatoprost SR 10 µg will provide approximately 98% power in showing noninferiority in 3 out of 3 timepoints with a noninferiority margin of 1.5 mm Hg, and 90% power in showing noninferiority in 2 out of 3 timepoints with a noninferiority margin of 1.0 mm Hg, assuming that both the between-eyes and the within-patient correlation coefficients are 0.5.

Assuming a premature discontinuation rate of 10%, approximately 160 patients are to be enrolled into this study and treated with Bimatoprost SR 10 µg. Additionally, there are approximately 50 patients who were enrolled before implementation of Amendment 3.

7.6 Interim Analyses

No interim analyses are planned.

8. Study Visit Schedule and Procedures

Patients who complete all study treatments will have up to 28 visits and 5 phone calls. The schedule includes the following:

- Screening (up to 28 days); Washout period of up to 56 days for both eyes; and Baseline visit (up to 3 days)
- SLT treatment (Day 1) and phone call (Day 2)
- Bimatoprost SR Cycle 1 administration (Day 4); Cycle 1 Day 2 safety visit; Cycle 1 Day 4 and Week 2 phone calls; and follow-up study visits at Weeks 4, 8, 12, and 15

- Bimatoprost SR Cycle 2 administration (to occur at Week 16 for all patients who meet retreatment criteria); Cycle 2 Day 2 safety visit; and Cycle 2 Day 4 and Week 2 phone calls
 - Patients who do not receive Cycle 2 administration at Week 16 will not attend the Cycle 2 Administration Day visit on Week 16, or the Day 2 Safety or Day 4 and Week 2 phone calls associated with administration at Week 16. For these patients, Cycle 2 may be performed at the investigator's discretion during an unscheduled visit after Week 16 and prior to the Month 12 visit if the retreatment criteria are met; in this case, inadequate control of IOP should be confirmed at another scheduled or unscheduled visit prior to initiation of Cycle 2. All Cycle 2 visits will apply at the time of the Cycle 2 administration.
- Follow-up visits at Weeks 20, 24, 28, 31, 36, 40, 44, 47, and 52; and Months 13, 14, 15, 16, 18, 20, 22, and 24/Exit
 - Regardless of the timing of Cycle 2 administration, all regularly scheduled visits should be completed. Cycle 2 visits should be scheduled such that the Administration Day and the Day 2 Safety Visit do not occur on the day of a regularly scheduled study visit. However, if the Cycle 2 Day 4 or Week 2 Phone Calls overlap with a regularly scheduled visit, perform the regularly scheduled visit.
 - Patients who receive the second administration of Bimatoprost SR at Week 16 and patients who never receive a second administration may, at the investigator's discretion, skip the visits at Months 13, 15 and 22 if the patient has received nonstudy IOP lowering medication in both eyes; has $\leq 25\%$ of each implant remaining in the eye; and in the investigator's clinical judgment, has no safety or other concern that would require the patient to attend these visits. Please note: as described in Section 4.5.2, each eye should be evaluated on an individual basis when determining the need for additional nonstudy IOP-lowering treatments; initiation of treatment in one eye should not automatically lead to initiation of treatment in the contralateral eye.

IOP evaluations will occur at Hour 0 (08:00 AM \pm 1 hour) in all patients. Selected patients at selected sites will have additional IOP measurements performed at Hour 2 (Hour 0 + 2 hours [\pm 30 minutes]) and Hour 8 (Hour 0 + 8 hours [\pm 30 minutes]).

The study visits should adhere as closely as possible to the schedule shown in [Table 2](#), [Table 3](#), [Table 4](#), [Table 5](#), and [Table 6](#).

